3.1.1. Rationale for Study Population

Part A will be conducted in participants with later-onset SMA who are 2 to \leq 15 years of age, inclusive, for the purpose of evaluating AEs.

Part B will include participants with both infantile-onset SMA (≤ 7 months of age) and later-onset SMA (2 to < 10 years of age). The infantile-onset SMA population was selected as the main population to evaluate efficacy based on the following considerations:

- The results of modeling and simulations showed that an improvement in CHOP-INTEND, which is administered in participants with infantile-onset SMA, may be possible with a higher dose.
- Data from Studies CS3B and CS4 show that improvement in efficacy occurs more quickly in younger participants with shorter disease duration.

Therefore, the infantile-onset SMA population may be more sensitive to a higher dose, and thus efficacy in Part B can be assessed at an earlier timepoint compared to participants with later-onset SMA. In addition, the choice of the infantile-onset SMA population allows the opportunity to leverage data from Study CS3B, which used the approved dose of 12 mg, as does the Control Group in this study.

Part C will enroll participants with SMA who have been receiving nusinersen treatment for at least 1 year prior to entry in this study across participants of all ages (Cohort 1) and participants ≥ 18 years of age (Cohort 2). Participants should be receiving nusinersen as per local label and have no missed doses in the last year prior to Screening. This part is designed to evaluate the safety of transitioning participants from the currently approved dosing regimen to the higher dosing regimen in a representative patient population.

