After 6 participants have completed the loading period (i.e., when the last participant has available safety data through the Day 64 visit), an IDMC will review the available safety data to recommend whether Part B can be initiated. If deemed necessary by the Sponsor, additional participants may be enrolled in Part A to ensure sufficient data are available for the IDMC review prior to enrollment of participants in Part B. Details regarding the IDMC review of data may be found in the IDMC charter. Meanwhile, participants in Part A will proceed to maintenance dosing without interruption. Note that the IDMC can recommend to stop the study based on the safety findings.

Part B will consist of a pivotal, double-blind, active-controlled treatment period with either 2 or 4 loading doses of nusinersen (for the 50/28-mg Group and Control Group, respectively) administered intrathecally followed by maintenance doses approximately every 4 months

thereafter. Approximately 99 participants with infantile- or later-onset SMA will be randomized in a 1:2 ratio to receive either the currently approved dosing regimen of 4 loading doses of 12 mg of nusinersen administered intrathecally (Days 1, 15, 29, and 64) followed by 2 maintenance doses of 12 mg on Days 183 and 279 (Control Group) or 2 loading doses of 50 mg of nusinersen administered intrathecally (Days 1 and 15) followed by 2 maintenance doses of 28 mg on Days 135 and 279 (50/28-mg Group). In order to maintain blinding, 1 sham procedure will be administered in the Control Group on Day 135 and 3 sham procedures will be administered in the 50/28-mg Group on Days 29, 64, and 183 to ensure the same dosing visit schedule as the Control Group. Participants will remain at the clinic for at least 24 hours after study treatment administration on Days 1 and 15; inpatient stays at other visits may occur based on the Investigator's discretion. If the primary reason for the inpatient stay is due to an AE or SAE, reporting requirements per Section 11.3 must be followed.

Randomization in Part B will be performed using IRT. For Part B, the randomization will be stratified as follows:

- For participants with infantile-onset SMA by disease duration: ≤ 12 weeks and > 12 weeks (time from age at symptom onset to age at informed consent)
- For participants with later-onset SMA by age at informed consent: < 6 years and ≥ 6 years

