12. STATISTICAL METHODS AND DETERMINATION OF SAMPLE SIZE

12.1. General Considerations

The objectives of the study, the endpoints to be analyzed, and the statistical hypotheses are listed in Section 4.

In Part B, the primary endpoint and a subset of the secondary endpoints will compare the 50/28-mg Group to participants who received sham control in Study CS3B; these analyses will be performed using the 50/28-mg Group within this study and the data from the Study CS3B Sham Control Group. A matching algorithm will be used to select a group of participants who are similar to the 232SM203 higher dose group. The remaining secondary endpoints will compare the arms within Study 232SM203 Part B (50/28 mg Group versus 12 mg Group). This is detailed further in the following sections.

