12.4.1. Analysis of the Primary Endpoint in Part B

CHOP-INTEND

The primary efficacy endpoint of change from baseline to Day 183 in CHOP-INTEND total score will be analyzed using the joint-rank methodology to account for mortality [Berry 2013]. This joint-ranking procedure allows for a statistical test of the treatment effect on the CHOP-INTEND total score while accounting for loss of data due to deaths. In this analysis, a participant's Combined Assessment of Function and Survival score will be calculated by comparing each participant to every other participant in the study, resulting in a score of +1 if the CONFIDENTIAL

outcome was better than the participant being compared, -1 if worse, and 0 if the same. The participant's score will then be calculated by summing up their comparison to all the other participants in the study. For example, if 2 participants complete the study up to Day 183, their comparison score will be based on the change from baseline in CHOP-INTEND total score at Day 183. A participant who dies prior to the Day 183 visit will rank lower than any participant who completes the study up to Day 183. Two participants who both die prior to the Day 183 visit will be ranked based on the time of death with longer time to death corresponding to the higher rank. Hence, in general, these comparisons will result in participants who die being assigned the worst scores and ranked according to the time of death. Multiple imputation will be utilized to impute a missing Day 183 value of CHOP-INTEND for participants who discontinued for a reason other than death or where it was not assessed. Participants who have an imputed or available Day 183 score will be ranked more favorably than participants who die. The ranked scores will be analyzed using an analysis of covariance model with treatment included as a fixed effect and adjusted for baseline CHOP-INTEND total score and disease duration.

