12.4.2. Analysis of the Secondary Endpoints in Part B

HINE Motor Milestone Responders

The difference in the proportion of responders between treatment groups will be compared using logistic regression with the number of motor milestones at Baseline, age at symptom onset, and disease duration at Screening as covariates. Should the number of responders be less than 5 in either group, Fisher's exact test will be used instead. If Fisher's exact test is used, the unconditional confidence interval for the difference in response rates will be provided [Santner and Snell 1980].

The proportion of HINE Section 2 motor milestone responders will be assessed at Day 183 for 50/28 mg versus sham.

Total HINE Section 2 – Motor Milestones

Change from baseline to Day 183 for 50/28 mg versus sham and change from baseline to Day 302 for 50/28 mg versus 12 mg will be analyzed using the same methodology as described for the primary endpoint.

Plasma Neurofilament

For plasma NF-L, if the baseline assessment is missing, then the first available assessment post dose within Day 2 will be used instead as baseline.

Values that are BLQ will be set to half of the diluted LLOQ.

Change in plasma NF-L from (ratio to) baseline to Day 183 will be analyzed for 50/28 mg versus sham, and change in plasma NF-L from baseline to Day 29 will be analyzed for 50/28 mg versus 12 mg using the same method as for the primary endpoint.

CHOP-INTEND

Change in CHOP-INTEND from baseline to Day 302 will be analyzed for 50/28 mg versus 12 mg using the same methodology as described for the primary endpoint.

Time to Death or Permanent Ventilation

Permanent ventilation is defined as tracheostomy or ≥ 16 hours of ventilation/day continuously for > 21 days in the absence of an acute reversible event (Appendix A).

An independent EAC will determine, in a blinded fashion, the date at which a participant is considered to have met the definition of an event. The procedures for reviewing and adjudicating events will be described in a charter.

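### The joint-rank and trimmed-mean models omit age at symptom onset, which the rank 2 responder model adjusts for, and the protocol gives no reason

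*Protocol*

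**What the plan says.** Section 12.4.1 specifies an ANCOVA on the joint ranks with treatment as a fixed effect, "adjusted for baseline CHOP-INTEND total score and disease duration". The supplementary trimmed-mean ANCOVA in the same section uses the same two covariates.

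Section 12.4.2 carries the primary method to the other joint-rank tests. The HINE total score (ranks 3 and 6) and Day 302 CHOP-INTEND (rank 5) are analyzed "using the same methodology as described for the primary endpoint". Plasma NF-L (ranks 4 and 7) is analyzed "using the same method as for the primary endpoint".

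The rank 2 responder model is different. It is a logistic regression with "number of motor milestones at Baseline, age at symptom onset, and disease duration at Screening as covariates".

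Three other statements bear on the point:

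- Section 5.1 defines disease duration, the stratification factor for infantile onset, as "time from age at symptom onset to age at informed consent".
- Section 3.1.1, explaining the choice of population, says that "improvement in efficacy occurs more quickly in younger participants with shorter disease duration".
- Section 12.1 describes how the sham group is formed: "A matching algorithm will be used to select a group of participants who are similar to the 232SM203 higher dose group". The pool is 37 and the minimum matched is 20 (Section 12.4).

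**The concern.** Ranks 1 and 2 compare the same infants with the same matched sham group at the same visit, both on motor outcomes, yet they adjust for different baseline variables. If age at onset is worth adjusting for at rank 2, the reader needs to know why it is not at rank 1 or in the tests that inherit its model.

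Two things are at stake. The sham group is external, so any prognostic difference that survives matching goes into the treatment contrast unless the model removes it. The 12 mg comparison is randomized, so what is lost there is precision. Testing is strictly sequential, and rank 5, the first 12 mg comparison, must succeed before ranks 6 to 11 can be claimed.

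**Working it through.** **1. Covariate sets in Table 8 order**

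| Rank | Control | Model | Covariates besides treatment |
|---|---|---|---|
| 1 | matched sham | joint-rank ANCOVA | baseline score, disease duration |
| 2 | matched sham | logistic | baseline milestones, disease duration, **age at onset** |
| 3, 4 | matched sham | as rank 1 | as rank 1, by reference |
| 5–7 | 12 mg | as rank 1 | as rank 1, by reference |

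Ranks 8 to 11 are log-rank tests stratified by disease duration.

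**2. Duration does not carry age.** By the Section 5.1 definition, age at consent = age at onset + duration. As an illustration, take two infants who both have 8 weeks' duration, with onset at 4 and at 20 weeks. They are 12 and 28 weeks old at consent (84 and 196 days). Both fall within the onset limit of 180 days and the consent limit of 210 days. A model with duration alone treats them alike. With onset age and continuous duration both in the model, age is adjusted for linearly.

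**3. The plan's own figure.** Section 12.11 gives 50 v at least 20, a 24-point difference, SD 8.8, a 23% survival benefit, two-sided 0.05, and power of at least about 99%.

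- Ignoring deaths, SE = 8.8 × √(1/20 + 1/50) = 2.33 and 24/2.33 = 10.3, so power is 1.000.
- Simulating the joint-rank ANCOVA with assumed sham survival of 60% or 70%, and 23 points higher on treatment, gives 0.9995 and 1.000.

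The stated power is reproduced. The difference detectable with 99% power is 2.33 × (1.960 + 2.326) = 9.98 points.

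**4. Sham comparison: imbalance left after matching.** Let R² be the share of residual variance that onset age explains, and d the imbalance in SD units. The protocol gives neither, so both are assumed. Bias in points = √R² × 8.8 × d. Type I error comes from 6,000 simulated trials per cell, 50 v 20, with 80% survival assumed in both arms.

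| R² | d | Bias (points) | Type I error without onset age | With onset age |
|---|---|---|---|---|
| 0.10 | 0.25 | 0.70 | 5.3% | 4.8% |
| 0.10 | 0.50 | 1.39 | 6.2% | 4.7% |
| 0.20 | 0.50 | 1.97 | 7.7% | 4.4% |

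A bias of 2 points is about 8% of the 24-point design effect (2/24).

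**5. 12 mg comparison: precision.** Inputs are 50 v 25 (Section 7.1), 5 points (the modeled gain in Section 3.1.2, not a stated design effect) and SD 8.8 (given for Day 183 and borrowed here for Day 302). Normal-approximation power is Φ(5/SE − 1.96), where SE = 8.8 × √(1 − R²) × √(1/25 + 1/50). At R² = 0 the SE is 2.156, so power is Φ(2.320 − 1.96) = 64.0%. The simulated joint-rank ANCOVA assumes 90% survival in both arms, with 6,000 runs per cell.

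| R² (assumed) | Normal approximation | Joint rank without onset age | Joint rank with onset age |
|---|---|---|---|
| 0 | 64.0% | 43.2% | 42.2% |
| 0.05 | 66.3% | 41.7% | 42.6% |
| 0.10 | 68.6% | 43.3% | 44.0% |
| 0.20 | 73.7% | 42.0% | 46.4% |

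The Monte Carlo standard error of each joint-rank figure is √(0.43 × 0.57/6000) = 0.64 points, so about 0.9 for a difference between two cells. The gains at R² of 0.05 and 0.10, and the drop at 0, are therefore within simulation noise. Only the gain of 4.4 points at 0.20 is clearly distinguishable.

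**The case against.** The strongest reply is that this is a choice of covariates and breaks no rule. The primary model adjusts for the endpoint's own baseline and for the stratification factor, and disease duration runs through the trimmed-mean and log-rank analyses too. Rank 2 is the exception, and different endpoints may have different models. The infants form a narrow group: two SMN2 copies, onset by 180 days, consent by 210 days. Section 3.1.1 speaks of younger participants when contrasting infantile with later onset, and does not mention onset age among Part B infants. Covariates for secondary tests may also be set out in the SAP, which is not at hand, and the baseline term must in any case change for HINE and NF-L.

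Most of this stands. It means the protocol nowhere calls onset age prognostic; that is inferred from its use at rank 2, with some support from Section 3.1.1. It does not explain why rank 2 alone needs the variable, and Section 12.4.1 does fix the primary list.

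Three stronger readings may tempt a reader, and the documents support none of them.

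- **Bias control against sham is given up.** Matching is the first line of control. Its variables are not legible, which is no defect of the plan, and may include age or age at onset. Only adjustment for what matching leaves is forgone.
- **Onset-age imbalance biases the dose comparison by a sizeable part of the 5-point gain.** That comparison is randomized. Chance imbalance is not bias, and the test's error rate already allows for it.
- **Power at rank 5 would rise appreciably.** The larger gains come from a comparison of means without deaths. Under the planned joint-rank test they shrink to about 1 to 4 points.

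**Conclusion.** The inconsistency is real and unexplained: the joint-rank and trimmed-mean models omit a pre-treatment variable that the protocol itself uses at rank 2, and disease duration does not replace it. The consequence is modest.

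Against sham, with assumed R² of 0.10 to 0.20 and imbalance of 0.25 to 0.5 SD left after matching, the bias is about 0.7 to 2.0 points and simulated type I error is 5.3% to 7.7% without the covariate. This would not alter the primary conclusion at 24 points. Against 12 mg the gain is precision only, about 1 to 4 percentage points of joint-rank power for assumed R² of 0.05 to 0.20, and none at R² of 0. These sizes rest on assumed R², imbalance and survival, and on simulations without multiple imputation. No figure stated in the protocol is wrong. The case for the change is that it costs almost nothing, and its clearest value is in the non-randomized comparisons at ranks 1, 3 and 4.

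**What to change.** In Section 12.4.1, add age at symptom onset to the covariates of the joint-rank ANCOVA and of the trimmed-mean ANCOVA. In Section 12.4.2, state that every joint-rank test in Table 8 uses the same set: the endpoint's own baseline, disease duration and age at symptom onset. Fix this before unblinding.

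If the sponsor prefers the shorter list, one sentence should say why rank 2 needs onset age and the joint-rank tests do not.

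The cost is one residual degree of freedom: from 66 to 65 with 50 v 20 (70 participants less intercept, treatment and two covariates), and from 71 to 70 with 50 v 25. No new data are needed, because age at onset is already required to derive disease duration.

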12.4. Methods of Analysis for Efficacy Endpoints

Within Part B to control the overall Type 1 error at a 2 sided alpha level of 0.05, a sequential testing procedure ranked in the order of the primary and secondary endpoints will be utilized. In this procedure, the primary endpoint of change in CHOP-INTEND total score from baseline to Day 183 for the Study CS3B Sham Control Group compared to the 50/28-mg Group will be tested. If this is statistically significant, then the first secondary endpoint of the proportion of motor milestone responders at Day 183 for the Study CS3B Sham Control Group compared to the 50/28-mg Group will be tested and so forth in the order of the remaining endpoints as detailed in Table 8. Inferential conclusions about each successive analysis require statistical significance of the prior one.

The statistical testing of the primary endpoint and a subset of secondary endpoints will use the Sham Control Group from Study CS3B. Within Study CS3B, there are 37 participants with an opportunity to attend the Day 183 visit.

algorithm will be used to select a group of snam participants from the pool of 37. The algorithm will attempt to match the largest number of participants and if unsuccessful, smaller pools will be selected and the minimum matched will be 20 participants.
The main analysis for the primary endpoint and secondary endpoints comparing nusinersen 50/28 mg to sham will be performed using the 50/28 mg participants in the ITT Set and the set of at least 20 sham participants selected via the matching algorithm.
The main analyses for secondary endpoints comparing 50/28 mg to 12 mg will be performed using the ITT Set.

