The trimmed-means method [Permutt and Li 2017] will be performed as a supplementary analysis. The analysis will be performed treating all dropouts and deaths as bad outcomes and trimming them out with other observed bad outcomes to form balanced comparison groups. In the trimmed mean approach, response scores are ranked from best to worst, and participants who died are considered as having worse outcomes than those who survived and completed the study. All response scores in the treatment group with high mortality/dropout rate will be retained. In the treatment group with the higher survival/completion rate, only the same proportion (as the survival rate in the high-mortality group) of the top response scores will be retained. The trimmed-mean difference can be interpreted as the difference between the top fraction of responses between the 2 groups. An analysis of covariance model will be fitted to the trimmed sample, with treatment as a factor and adjusting for covariates of baseline score and disease duration to obtain the adjusted mean difference. The pvalue associated with the adjusted-difference test statistic will be calculated using a reference distribution generated by a rerandomization procedure.

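### The supplementary trimmed-means analysis trims deaths and dropouts alike but sets the retained fraction by survival alone, and its re-randomization p-value needs relabelling for the sham comparison

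*Protocol*

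**What the plan says.** Section 12.4.1 makes the joint-rank test the primary analysis and adds trimmed means as a supplement. The supplement is described as "treating all dropouts and deaths as bad outcomes and trimming them out with other observed bad outcomes", with the aim of obtaining balanced groups. The arm with more deaths and dropouts keeps all its response scores. In the other arm, "only the same proportion (as the survival rate in the high-mortality group) of the top response scores will be retained". An analysis of covariance on the trimmed sample, adjusted for baseline score and disease duration, gives the adjusted difference. The p-value rule follows: "The pvalue associated with the adjusted-difference test statistic will be calculated using a reference distribution generated by a rerandomization procedure".

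The contrast is with an external group. Section 12.1 says that "these analyses will be performed using the 50/28-mg Group within this study and the data from the Study CS3B Sham Control Group", and that "A matching algorithm will be used to select a group of participants who are similar to the 232SM203 higher dose group". Section 12.4 gives the pool ("Within Study CS3B, there are 37 participants with an opportunity to attend the Day 183 visit") and the floor ("the minimum matched will be 20 participants"). The only randomization in Part B is between 12 mg and 50/28 mg. Section 5.1 says: "Approximately 99 participants with infantile- or later-onset SMA will be randomized in a 1:2 ratio".

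**The concern.** There are two separate problems in one short paragraph.

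First, the trimming rule is inconsistent. A trimmed mean compares the same top fraction of each arm. The worse arm loses its deaths and its dropouts, so what remains is its completion fraction. The other arm is cut to a fraction that ignores dropouts. The result is then to be read as a difference between matching top fractions, which it is not once the worse arm has a dropout.

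Second, the term re-randomization implies an allocation scheme that can be re-run. None exists between 50/28 mg and CS3B sham, so a reader of the results could credit the p-value with a design basis that it lacks.

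The stake is limited but real. The joint-rank test works on ranks and Section 12.4.3 offers only descriptive summaries. This is therefore the only adjusted between-group difference in CHOP-INTEND points described for the primary endpoint, and it is likely to be quoted as the effect size.

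**Working it through.** **Inputs from the protocol (Sections 12.4 and 12.11).** 50 participants on 50/28 mg; at least 20 matched sham from a pool of 37; SD 8.8; planned difference 24 points; survival benefit 23% (read as percentage points); 2-sided 0.05. Sham survival, dropout rates and any between-study shift are not given, so ranges are assumed.

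**The plan's own figure.** No figure is given for trimmed means. The nearest is the power of the primary test, stated as at least about 99%. The standard error is 8.8 × √(1/50 + 1/20) = 2.33, and 24 / 2.33 = 10.3, so a simple two-mean comparison has power above 0.999. A joint-rank simulation (deaths ranked worst, t-test on ranks, no covariates, 4000 runs) gives 0.989 at sham survival 50% and 1.00 at 60%, 70% and 77%. The stated power reproduces; sample size is not in question.

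**Step 1: the fractions.** Let the worse arm have survival s and non-death dropout d. Its observed scores are the fraction c = s − d. The written rule keeps the fraction s of the other arm. The mismatch is s − c = d, which is zero only if d = 0.

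**Step 2: the size.** For a normal outcome with missing scores counted as worst, the mean of the top fraction p lies φ(z)/p standard deviations above the full mean, where z = Φ⁻¹(1 − p). With a common SD the true difference cancels, and the rule shifts the estimate (50/28 mg minus sham, sham the worse arm) by

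8.8 × [φ(z_s)/s − φ(z_c)/c].

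Example: s = 0.70, d = 0.10, c = 0.60. The terms are 0.497 and 0.644, so the shift is 8.8 × (0.497 − 0.644) = −1.3 points. The written rule keeps 50 × 0.70 = 35 scores; a completion rule would keep 50 × 0.60 = 30.

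| Assumed sham survival | Dropout 0% | 5% | 10% | 15% |
|---|---|---|---|---|
| 60% | 0 | −0.67 | −1.36 | −2.07 |
| 70% | 0 | −0.64 | −1.30 | −1.96 |
| 77% | 0 | −0.64 | −1.29 | −1.93 |

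The sign would reverse if 50/28 mg were the worse arm. The table also needs the better arm to have enough observed scores to reach the fraction s. With a 23-point survival benefit it does, provided its own dropout is at most 23 points.

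**Step 3: the p-value.** A simulated permutation test (20 versus 50, no drug effect, 70% survival and 10% dropout in both groups unless stated, trimming redone in every permutation, no covariates, 600 runs of 299 permutations) gives these rejection rates at nominal 5%:

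- Exchangeable groups: 5.2% with the completion rule, 5.5% with the survival rule.
- Assumed between-study shift of 2, 4 and 6 points (completion rule): 8%, 15% and 32%.
- A 4-point shift plus 10 points better survival on 50/28 mg (completion rule): 36%.

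The test therefore holds its level when the groups are exchangeable and not otherwise. The survival-rate wording does not by itself inflate the error rate; it distorts the estimate.

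**The case against.** The strongest reply is that the survival-rate phrase is shorthand. The same paragraph refers to mortality and dropout together when naming one arm and to survival and completion together when naming the other, so the intent is fairly clear, and with no dropout the two readings coincide. That is probably right about intent. But the operative clause is the one that a programmer would follow, and it names deaths only.

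It is also true that the shift is modest beside the planned 24 points (2.1 / 24 is about 9% at the upper end), that it works against the sponsor's regimen when sham is the worse arm, and that the analysis is supplementary and absent from the Table 8 test sequence.

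On the p-value, several stronger readings are tempting and should be resisted:

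- A reader might infer that no valid reference distribution exists. A permutation distribution exists and keeps its level under exchangeability. The primary analysis of covariance on ranks has no randomization basis for this contrast either.
- A reader might infer that the matched set is held fixed. The protocol does not say how the reference distribution is built or whether matching is repeated, and that detail may belong in the SAP.
- A reader might size between-study drift from the untrimmed standard error of 2.33, which gives rejection rates of about 14% and 40% at shifts of 2 and 4 points. That calculation has no deaths, dropouts or trimming; the trimmed test gives about 8% and 15%.
- Drift affects every comparison with CS3B sham. It is not a fault of the re-randomization step.

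Section 12.4.2 applies the primary endpoint's methodology to 50/28 mg versus 12 mg. If that includes trimmed means, re-randomization is legitimate there.

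**Conclusion.** The point holds as a correction to a supplementary analysis. The trimming rule contradicts its own aim whenever the arm with more deaths and dropouts has any non-death dropout. The shift is about 0.6 to 2.1 points against 50/28 mg for assumed sham survival of 60% to 77% and sham dropout of 5% to 15%. This rests on a normal outcome with common SD 8.8, missing scores counted as worst, sham as the worse arm and no covariate adjustment.

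The re-randomization part is narrower. For the sham contrast the procedure is a permutation test conditional on exchangeability after matching, and it should be called that. Nothing here touches the primary joint-rank decision, the Type 1 error or the sample size.

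**What to change.** Make two wording changes in Section 12.4.1.

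1. In the trimming clause, replace the survival rate of the high-mortality group with the completion rate (alive with an observed Day 183 score) in the group with the higher mortality/dropout rate.
2. For 50/28 mg versus matched sham, describe the p-value as coming from a permutation test that assumes exchangeability after matching. Reserve the term re-randomization for any use in 50/28 mg versus 12 mg.

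The cost is two edited sentences and a matching line in the analysis program. The corrected rule keeps fewer scores in the better arm, for example 30 rather than 35 of 50 at 70% survival and 10% dropout.

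A bootstrap that repeats the matching is not required. It would not remove drift, and resampling the 37 sham infants yields on average only 37 × (1 − (36/37)^37) = 23.6 distinct infants, close to the floor of 20 that must be matched.
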